2. CHARACTERISTICS OF STUDY POPULATION

2.1 Subject Characteristics

Asthma and its morbidity disproportionately affect minority children of low-income families in inner cities, where asthma severity has increased and poses serious challenges to achieving adequate asthma control.⁵ Disparate burdens of asthma and its adverse outcomes among minority children have been consistently documented in the past 20 years.^{4, 23-25} In 2010, asthma prevalence in black children under 18 years was twice that of white youths; children in families below the poverty threshold as defined by the US Census Bureau were 1.5 times more likely to report current asthma than those in families at or above 200% of the poverty line.² Compared with white youth, black inner-city children are 4 and 3 times more likely to have asthma-related ED visits and hospitalizations respectively.⁴ The three cities where the study will take place, Buffalo, NY; Baltimore MD; Memphis TN demonstrate high rates of pediatric asthma, high health care utilization and high morbidity and mortality rates, thus this study will take place in these cities that are most likely to benefit from a proposed intervention.

a) Number of Subjects:

A total of 378 adolescents (12-17 years) and 42 adolescent peer leaders (16-20 years) will be recruited for this study. The sample size (N=378) is based on the power analysis using a novel method developed by Roy et al.²⁶ for a 3-level hierarchical longitudinal design based on the program "RMASS." This method has the advantage of incorporating three levels from the sites and repeated-measures from each subject with random-effects of the time trends at both the subject- and site-level, which are assumed to be equivalent in terms of sampling proportions, number of groups and differential attrition rates over time. In this proposed study, quality of life, the primary outcome, was used to estimate the sample size. Using data from the previous study,²⁷ the longitudinal trajectories of quality of life and its treatment-by-time interactions based on subject-level randomization were modeled: the estimated treatment*time interaction coefficient was 0.6 units, estimated SDs for error was 15, and the random-slope was 1.76. These estimated values with a Type-I error rate (alpha) of .05 yielded a total sample size of 276 that would detect a

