time trend over eight time points (T1-T8) between groups with a power of .80. This sample size was estimated on the assumption that the analyses use multi-site hierarchical 3-level linear mixed-effects models. In the earlier study, the attrition rate of the inner-city subsample (n=55) was 27% including those who failed to attend the camp program (n=13, 23%) and those lost to follow-up (n=2, 4%). To compensate for a possible attrition rate of 27%, the total sample size was increased to 378 (126 for each site; 63 each of two groups).

b) Gender and Age of Subjects:

Recruitment will not be limited on gender. Based on epidemiological data, we will focus on adolescents from 12-17 years of age for campers and 16-20 years of age for peer leaders.

Participants will be stratified by gender and age (younger 12-14 years, older 15-17 years), which emerged as influential covariates in the PI's earlier study. Within each of four blocks generated by each combination of these two covariates, each subject will be randomly assigned to either group using a computer-generated randomization table. Stratified randomization will ensure a similar number of subjects representing each block in the two treatment groups, balancing the influence of age and gender. Stratified randomization will be done separately for each site, and centrally coordinated and managed. Within the treatment group, participants will be assigned to subgroups based on their age [younger (12-14 years) and older groups (15-17)] to allow the study team to adjust the levels of difficulty/complexity of program content delivered at the camp. In doing so, we will attempt to enhance participants' understanding of the information covered in the program. In the previous study, we found no differences in study outcomes or camp satisfaction between gender-matched groups and co-ed groups, so subgroups will be gender-mixed.

c) Racial and Ethnic Origin:

Enrollment of participants will not be restricted to any racial or ethnic groups. By recruiting participants from three cities with high prevalence and incidence of pediatric asthma, (again based on epidemiological data) we anticipate the sample demographic to have a higher proportion of minority populations representative of the neighborhoods targeted (Buffalo, Baltimore and Memphis.)

d) Vulnerable Subjects:

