4. METHODS AND STUDY PROCEDURES

4.1 Study Procedures and Assessments

Design: This study will use a two-group randomized controlled design implemented in three metropolitan cities: Buffalo, NY, Baltimore, MD, and Memphis, TN. The project coordinator and a research assistant in each city who are not involved in direct patient care of teens with asthma will be responsible for recruitment and consent process taking place in each site. Peer leaders will attend a three-day intense training session that will take place prior to camps, lead small-group instructional activities at a one-day camp (PLASMA group) and follow up their group members bimonthly for 15 months. Camp participants from each site (n=126) will be randomly assigned to the peer-led (PLASMA) group or the adult-led (control) group. Upon enrollment, participants will be stratified by gender and age (younger 12-14 years, older 15-17 years), and randomly assigned to either group within each of four blocks generated by the combination of gender and age strata. Each group will attend a separate day camp where an asthma self-management program will be implemented either by peer leaders (intervention) or healthcare professionals (control). After the camp, the intervention group will receive peer-leader contacts bimonthly for 14 months using phone calls or other communication technologies (e.g., emails, or short-message system (e.g., texting) of teens' choice. Adult instructors (healthcare professionals) will contact the control group bimonthly for 14 months using similar methods, but different contact topics.

Both groups (intervention and control – more details below) will provide data at enrollment (T1), 3 months later (T2), immediately following the camp (T3), and at 3-, 6-, 9-, 12-, and 15-months post-camp (T4-T8).

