10. DATA ANALYSIS AND DATA MONITORING

10.1 Planned Statistical Analysis: Analyses will be performed using SAS, and R⁵⁶ will be used as analysis software to ensure the validity and reproducibility of the results. We will perform descriptive statistics on each outcome measure to look for abnormality and outliers. If a measure is not normally distributed, transformation will be applied. We will identify and investigate outliers for sources of errors, and conduct preliminary analyses on data distribution and bivariate correlations to determine the appropriate statistical model as well as the final interpretation of the results. We will investigate missing data with pattern analysis for data missing completely at random (MCAR), missing at random (MAR) or missing not at random (MNAR), and use statistical methods appropriate for each type such as maximum likelihood and multiple imputation to impute missing values so full analysis can be performed with sensitivity. We will compute Cronbach's alphas for psychometric measures, and assess construct validity using exploratory or confirmatory factor analysis when appropriate. The PLASMA and control groups will be compared on baseline data to determine any systematic differences; if any are found, analyses will include the variables as covariates in the model to adjust for the imbalances.

Aim 1: A multi-site hierarchical three-level linear mixed-effects model,^{26, 56, 57} where level 1 represents repeated measures, level 2 = subject, and level 3 = site, will be used to analyze treatment differences and treatment-by-time interaction described in the following notation by Hedeker and Gibbons.⁵⁷

Aim 2: The mediating effects will be examined mainly using the mediation methods of Baron & Kenny.⁵⁸ When found significant, a multiple mediation analysis⁵⁹ procedure will be used to further determine whether the effect of PLASMA on quality of life is mediated jointly by multiple exploratory outcomes.

Aim 3: Moderating effects will be examined by multiple linear models and generalized linear models described in Berridge and Crouchley⁵⁶ or Chen and Peace⁶⁰ along with the above multi-site hierarchical three-level linear mixed-effects models.

Aim 4: This aim will be tested by applying the multi-site hierarchical two-level linear mixed-effects models described in the analysis for Aim 1, with level 1 representing longitudinal measurements and level 2 sites.

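### The Aim 1 model, as far as the text shows, leaves the pre-camp treatment difference free, so the primary comparison does not make full use of the T1 and T2 quality-of-life data

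*Combined protocol and SAP*

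**What the plan says.** Section 10.1, Aim 1, plans a mixed model with repeated measures at level 1, subject at level 2 and site at level 3, which "will be used to analyze treatment differences and treatment-by-time interaction". It then refers to notation that does not appear in the text available.

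Section 4.1 states that both groups "will provide data at enrollment (T1), 3 months later (T2), immediately following the camp (T3"), followed by visits at 3 to 15 months after the camp (T4–T8). Section 4.4 describes the second assessment as three months pre-camp. Section 7.2 gives a total span of 21 months. T1 and T2 therefore both precede any program content, and both are responses in the model: the sample size in Section 2.1a targets a "time trend over eight time points (T1-T8) between groups with a power of .80".

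H1 (Section 1) is about greater improvement over time, so treatment-by-time is the primary contrast. Section 10.1 also compares the arms at baseline and adds a variable as a covariate only where a difference is found. No visible text sets the pre-camp means equal or makes baseline quality of life a standing adjustment.

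**The concern.** With time counted from T1, a treatment main effect beside treatment-by-time is the T1 difference between randomised arms. Its expectation is zero among all randomised. Estimating it lets chance T1 imbalance feed into the estimated change and adds variance. It should also not be read as a program effect, although the text lists treatment differences among the quantities to be analysed.

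The conditional covariate rule does not settle this. It makes baseline handling depend on the data, and if T1 quality of life were flagged it would be both a response and a covariate in one model.

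What is at stake is precision on the primary outcome, from data that the trial collects anyway.

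**Working it through.** **Inputs from Section 2.1a.** Interaction: "the estimated treatment*time interaction coefficient was 0.6 units". Variability: "estimated SDs for error was 15, and the random-slope was 1.76" (1.76 read as an SD). Error rate and size: "a Type-I error rate (alpha) of .05 yielded a total sample size of 276". Power .80, eight time points.

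**Not given, so assumed.** Intercept SD 10–25; intercept-slope correlation 0, varied from −0.3 to +0.3; time unit per visit (0–7) or per month (0–21). Site terms and dropout are left out.

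**The plan's own figure.** Per-subject slope variance is V = 1.76² + error variance / Σ(t − mean t)², where the sum is 42 (visits) or 378 (months). Per arm, n = 2(1.96 + 0.84)²V / 0.6², two-sided.
- Error SD 15, visits: V = 3.098 + 225/42 = 8.45; N = 738.
- Error SD 15, months: V = 3.098 + 225/378 = 3.69; N = 324.
- 15 read as a variance, months: V = 3.098 + 15/378 = 3.14; N = 274, or 276 when rounded to 46 per arm per site.

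Only the last reading matches 276. The program used also needs inputs that are not printed (site variance, attrition pattern, time coding), so this does not show that 276 is wrong. The attrition step reproduces: 276/0.73 = 378.1.

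**Linear slope, only T1 constrained.** Let I = Z′W⁻¹Z per arm, with Z = [1, t] and W = ZDZ′ + 225·identity, D being the covariance of intercept and slope. The slope variance is (I⁻¹)₂₂ with the T1 difference free and 1/I₂₂ with it fixed at zero. At zero correlation:

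| Time unit | Free | Constrained, intercept SD 10 / 15 / 20 / 25 | Cut |
|---|---|---|---|
| Visit | 8.45 | 6.64 / 7.35 / 7.74 / 7.97 | 6–22% |
| Month | 3.69 | 3.49 / 3.57 / 3.61 / 3.64 | 1.5–5.5% |

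Correlations of −0.3 to +0.3 widen the range to about 0–35%. If 15 is a variance and time is in months, the cut is about 0% at zero correlation and at most 9.7% with correlation.

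**Categorical visits, common means at T1 and T2.** The unconstrained T1-to-T8 change has per-arm variance 1.76²·t₈² + 2·225, with t₈ the time of T8:
- visits: 151.8 + 450 = 601.8
- months: 1366.0 + 450 = 1816.0

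With common pre-camp means, the variance is that of the T8 response given T1 and T2: W₈₈ − c′A⁻¹c. Here A is the covariance of T1 and T2, and c is their covariance with T8. Example (visits, intercept SD 10): W₈₈ = 100 + 151.8 + 225 = 476.8; A has diagonal 325 and 328.1 and off-diagonal 100; c = (100, 121.7); c′A⁻¹c = 58.6; result 418.2; cut 1 − 418.2/601.8 = 30.5%.

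| Time unit | Unconstrained | Constrained, intercept SD 10 / 15 / 20 / 25 | Cut |
|---|---|---|---|
| Visit | 601.8 | 418.2 / 436.4 / 447.0 / 453.2 | 25–31% |
| Month | 1816.0 | 1443.3 / 1444.5 / 1445.2 / 1445.7 | 20% |

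At correlations of −0.3 and +0.3 the cut is 22–37% (visits) or 21–26% (months). With T1 alone constrained, the variance is W₈₈ − W₁₈²/W₁₁; in the example 476.8 − 100²/325 = 446.0. At zero correlation the cut is then 10–26% (visits) or 3–9% (months), so part of the gain rests on T2.

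**Scope of the comparison.** The 20–31% compares two analyses of the same T1-to-T8 contrast. If the arm difference were exactly linear from T1, the planned slope extrapolated to T8 would have variance 7² × 8.45 = 414 (visits) or 21² × 3.69 = 1628 (months). Against that, the constrained categorical contrast is slightly less precise per visit (418–453) and more precise per month (about 1445).

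**The case against.** The strongest reply is that nothing is thrown away. A reader might infer that the planned test discards baseline; the documents do not support that. T1 is in the likelihood and informs the slope. Dropping it would lower power at N = 276 from .403 to .321 (visits, SD 15), from .737 to .704 (months, SD 15) or from .803 to .801 (months, variance 15). This stands: T1 is used, though not fully.

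The model equation is also missing, so a constraint in the notation cannot be ruled out. That stands, and is why the point is worded conditionally.

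A reader might take T1 as a covariate to be an equivalent remedy. For the linear-slope test it is not: with T2–T8 as outcomes and both treatment terms kept, the slope variance rises from 8.45 to 11.13 (visits) or from 3.69 to 3.99 (months).

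Nor is the constraint always a gain. If the arm difference is zero through T3 and then grows linearly, fixing only T1 under linear time makes the z-statistic 2–8% smaller (months, zero correlation, intercept SD 10–25). Because T2 precedes the camp, a linear effect from T1 already implies a difference before any program. Common means at both pre-camp visits, with time not forced to be linear from T1, avoid this.

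Finally, the zero difference holds among all randomised. Section 5 withdraws teens who miss the camp (23% of the earlier inner-city subsample, Section 2.1a), and Sections 7 and 8 destroy data on a withdrawal request. If no-shows are left out of the analysis, the zero no longer follows. This shapes the fix but does not defeat it.

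**Conclusion.** The point holds as one of efficiency. On the visible text, pre-camp differences are left free and baseline adjustment depends on finding an imbalance, so the primary comparison is less precise than the data allow. Leaving the difference free neither biases the interaction nor inflates type I error.

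The size is about 20–31% of the variance of the T1-to-T8 contrast, under error SD 15, slope SD 1.76, an assumed intercept SD of 10–25, zero correlation, and no arm difference at T1 or T2. For a linear slope with only T1 constrained it is 1.5–22%, and near zero under other readings.

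A reader might turn this into a gain on the planned power of .80. The documents do not allow that: with these inputs and N = 276, the slope formula gives .40 (visits) or .74 (months) before any constraint, and the intercept variance is not stated.

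Equality at T1 follows from randomisation. Equality at T2 also needs nothing to differ between arms before the camp, which fits Section 4.1 and the concealment described in Section 3.2.

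**What to change.** Pre-specify in Section 10.1, before unblinded data are seen:
- Visit as categorical, or time piecewise from the camp, with one common mean for both arms at T1 and one at T2.
- Treatment-by-visit terms from T3 on, with the treatment effect defined by named post-camp contrasts.
- T1 and T2 data from every randomised teen, camp no-shows included, except data that must be destroyed on request.
- The same model for the H2 scales measured at every visit.
- A sensitivity analysis with only T1 constrained, in case the arms could differ by T2.

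Write out the model equation, so that the time origin and the meaning of each treatment term are explicit. State that this handling of baseline quality of life does not depend on the baseline comparison.

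The cost is a short SAP entry and a change to the model code. No extra visits, measures or participants are needed.

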Hypothesis: We hypothesize that: relative to the control group, the PLASMA group will report greater improvement over time in (H1) quality of life (primary outcome), and (H2) asthma knowledge, attitudes, outcome expectations, self-efficacy, self-management skills, and asthma control, FEV1 (exploratory outcomes). (H3) The post-PLASMA scores on outcome measures will be higher than pre-program scores from both treatment groups.

- 2) To examine the mediating effects of the secondary outcomes (knowledge, attitudes, outcome expectations, self-efficacy, self-management skills, asthma control, and FEV1) on the primary outcome (quality of life) of the intervention.
- 3) To examine the moderating effects of personal factors (e.g., age, sex, family support) on primary and secondary outcomes of the intervention.
- 4) To evaluate the effects of PLASMA on primary and exploratory outcomes in peer leaders (16-20 years).

Hypothesis: We hypothesize that the peer leaders (n=42) will report significant improvement in quality of life (primary outcome) and secondary outcomes (knowledge, attitudes, outcome expectations, self-efficacy, self-management skills, asthma control and FEV1) over the course of 15 months.

- 5) To determine the economic impact of the intervention. This aim will be accomplished by (5a) measuring the direct healthcare costs and total costs of the PLASMA program, as compared with the control group; (5b) performing net cost analyses for each type of costs; and (5c) estimating cost-effectiveness ratios of the PLASMA group compared with the control.

Hypothesis: We hypothesize that the direct and overall costs per participant in the PLASMA group will be less than costs per participant in the control group, or cost neutral.

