(f) Medication Adherence-Self Report (AD-S): To assess medication adherence, we will use the Horne's Medication adherence report scale, and also ask teens to report doses missed in the prior 2 weeks. These self-report measures will be administered for each assessment point.

(g) Medication Adherence-Objective (AD-O): to obtain objective adherence data, we will use dose counters that are integrated into medication canisters. Based on personal communication with a local healthcare provider, we learned that almost all inhaled steroids now include counters, and 99% of children used medication that included integrated counters. Participants will bring their medication canisters to an appointment with the study nurse, who will document the number of doses on the teens' control medication inhaler (or count remaining pills for oral medications, i.e.; Singulair). Two weeks later, teens will use their mobile phone to take and send the picture of their inhaler displaying the counter number. For those without a mobile phone, in-person appointments or home visits will be arranged to re-measure the doses used. Based on the prescribed regimen, we will calculate adherence (#actuations / #prescribed) over the prior 2 weeks. Given the labor and time intensive nature of the assessment, we will obtain objective adherence data only twice, at baseline and 15-months assessments, which will provide the snapshot of adherence before and after study participation

(h) Asthma Control Test (ACT), a 5-item clinical scale, assesses asthma control based on the frequency of daytime and nighttime symptoms, degree of activity limitation, and use of SABA in the past 4 weeks, per 2007 NHLBI Guidelines. Cronbach's α was .71 in our previous study.²⁷ Items will also be examined individually.

(i) Asthma Exacerbation Checklist (AEC): This will assess the indicators of exacerbation including (1) systemic corticosteroids for asthma for at least 3 days; (2) asthma-specific hospital admission; and (3) asthma-specific ED visits. The self-report asthma exacerbation checklist will be used for all the assessment time points.

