(j) Peak Expiratory Flow Rate (PEFR): we will use commercial electronic peak flow meters (Piko-1™). The Piko-1 (Ferraris Respiratory, Louisville, CO, USA) measures peak expiratory flow and FEV1, and it can store up to 96 measurements that are date- and time- stamped. Three color zones are visible on the display of the device: green for >80%, yellow for 50-80% and red for <50% of an individual's best. Stored data in the Piko-1 can be downloaded to a computer. The device is powered by batteries, lasting about 2 years if used 6 times a day. Values from the Piko-1 have shown high correlations ($r=0.93-0.95$) with those from a reference spirometer, indicating

the acceptable accuracy of the device.^{50, 51} The Piko-1 will be provided to 20 randomly selected participants from each site (10 from each treatment group) who will be instructed to use the device at least once a day. The RAs will make home visits every 3 months to download the stored data to a computer. For the rest of the sample, we will provide a manual peak flow meter with training on its use and instruct them to use it daily and record the values in a log as we proposed in the application, because this is part of self-management routines that we will attempt to reinforce through our training programs.

(k) Spirometry will be performed using a portable KoKo® spirometer (Pulmonary Data Service; Louisville, CO). Predicted values will be based on the equations of Polgar. The primary variables will be forced vital capacity (FVC) and FEV1, to be measured twice, at the camp and 15-months post-camp. Respiratory therapists at each site will be trained to perform the test in accordance with the ATS/ERS standardization of spirometry⁵² prior to conducting the tests, and data will be interpreted in collaboration with a pulmonologist at the study center.

Moderators:

(l) Perceived Family Support (PFS): We found that family support influenced quality of life and asthma control in adolescents.⁵³ This 20-item scale measures individuals' perception of their family fulfilling their needs for support, information and feedback. Construct and criterion validity was demonstrated.⁵⁴ Cronbach's α in our previous study was .85. **(m) Sociodemographic Form (SDF)** will be completed by parents to indicate adolescents' race, age, sex, insurance type, parental education and annual family income.

Table 1: Study measures for each assessment point

PRIMARY OUTCOME	PAQL	EXPLORATORY OUTCOMES												MODERATOR	

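### Aim 1 names one linear mixed model and gives no method suited to the outcomes read only twice (spirometric FEV1, objective adherence) or to exacerbation events

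*Combined protocol and SAP*

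**What the plan says.** Section 10.1 specifies one method for Aim 1: a linear mixed-effects model with repeated measures, teen and site as its three levels, which "will be used to analyze treatment differences and treatment-by-time interaction described in the following notation". The notation is not shown in the copy reviewed, so the random effects cannot be read from it. Two general rules precede the aims: non-normal measures are transformed, and preliminary analyses of distributions and correlations guide the choice of model. Neither is tied to a particular outcome. Generalized linear models are named for Aim 3 (moderation) only.

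Hypothesis H2 under Aim 1 (Section 1) covers "asthma knowledge, attitudes, outcome expectations, self-efficacy, self-management skills, and asthma control, FEV1 (exploratory outcomes". Section 4.1 lists further exploratory outcomes, among them objective adherence and the exacerbation checklist. Its text gives these schedules:

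- Objective adherence, item (g): "we will obtain objective adherence data only twice, at baseline and 15-months assessments".
- Spirometry, item (k): "The primary variables will be forced vital capacity (FVC) and FEV1, to be measured twice, at the camp and 15-months post-camp".
- Exacerbations, item (i): "The self-report asthma exacerbation checklist will be used for all the assessment time points". The indicators are systemic steroid courses, asthma admissions and asthma ED visits.

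Table 1 could not be read reliably in the copy reviewed, so these schedules rest on the text alone.

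Random time trends are mentioned only in Section 2.1 a), where the sample-size method is described as having "random-effects of the time trends at both the subject- and site-level". Quality of life is the outcome used there.

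**The concern.** A treatment-by-time model suits a scale collected at eight visits. It is less apt for an outcome with two readings, where a trend is just one difference, and for an outcome made of events. The plan does not say how the model is adapted in either case, so the choice would be made after the data are in hand.

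Two things are at stake. For FEV1 and objective adherence, the stated interaction gives away precision that the first reading, already being collected, could supply. For exacerbations, the result would be a slope on a raw or transformed event score, which a clinician cannot read as a rate or a risk.

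**Working it through.** The plan gives no power or precision figure for these outcomes. Its sample size concerns quality of life over eight time points and is not used here.

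**1. What two readings can identify.** Let the readings be at times 0 and t, with intercept variance A, slope variance B, intercept-slope covariance C and residual variance E:

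- Var(first) = A + E
- Cov(first, last) = A + tC
- Var(last) = A + 2tC + t²B + E

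That is three observable quantities.

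| Random effects | Parameters | Rank | Identified? |
|---|---|---|---|
| Intercept + residual | 2 | 2 | yes |
| Uncorrelated intercept and slope + residual | 3 | 3 | just |
| Correlated intercept and slope + residual | 4 | 3 | no |
| The same, with eight readings | 4 | 4 | yes |

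**2. What the treatment-by-time term becomes.** With both readings present, the fitted interaction is (mean last − mean first) in the PLASMA arm minus the same difference in the control arm. That is the change-score comparison. A check on simulated data (276 teens, three sites, illustrative between-teen SD 10, residual SD 5, true interaction 2) gave:

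- Random-intercept model: 2.2346 (SE 0.8430).
- Change-score comparison: 2.2346 (SE 0.8430).
- Correlated intercept-slope model: 2.2346 (SE 0.8430). Its slope variance (4.07 to 4.39) and residual variance (22.3 to 22.5) depended on the optimiser, at an equal log-likelihood.

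The treatment estimate is therefore available in every case; only the variance components are not separable in the last. A mixed model could recover the adjustment gain by constraining the first-reading means to be equal across arms. Aim 1 states no such constraint and asks for a treatment difference as well as an interaction.

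**3. Precision given away.** Assume equal variances at the two readings, correlation r between them, and a first reading unaffected by arm. In units of the common variance, a change score has variance 2(1 − r) and the baseline-adjusted value has 1 − r². The ratio is (1 − r²) / [2(1 − r)] = (1 + r)/2.

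| Assumed r | Ratio (1 + r)/2 | Equivalent extra teens, 1/ratio − 1 |
|---|---|---|
| 0.3 | 0.65 | 54% |
| 0.5 | 0.75 | 33% |
| 0.7 | 0.85 | 18% |

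The documents give no r for either outcome. The gain shrinks towards zero as r approaches 1.

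**4. Exacerbations.** A yes/no indicator takes two values, and any transformation of it still takes two. For counts the documents give no event rate, so a range of Poisson rates is assumed. The share of zeros is exp(−rate) and the skewness is 1/√rate; skewness after log(1 + x) comes from simulation.

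| Assumed events per 3 months | Zeros | Skewness | Skewness after log(1 + x) |
|---|---|---|---|
| 0.05 | 95% | 4.5 | 4.3 |
| 0.1 | 90% | 3.2 | 2.9 |
| 0.3 | 74% | 1.8 | 1.3 |
| 0.5 | 61% | 1.4 | 0.8 |
| 1.0 | 37% | 1.0 | 0.1 |

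The transformation does little when events are sparse and works only when they are frequent. Even then the estimate is a difference on a log(1 + x) scale, not a rate ratio.

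**The case against.** A reader might infer that the Aim 1 model cannot be fitted to FEV1 or objective adherence at all. The documents do not support that. The Aim 1 wording is met by a random-intercept model, which two readings identify. The random time trend comes from the quality-of-life sample-size text, and the missing notation cannot settle which random effects Aim 1 intends. There is some support for a random-trend reading, because the Aim 1 sentence cites the same sample-size reference, but it is not certain.

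Other limits also stand. H2 names FEV1 but neither objective adherence nor exacerbations, so the plan does not expressly commit every outcome to this model. The sentence on choosing a model after preliminary analyses leaves room for another method. FEV1 is not confined to spirometry: the electronic peak flow meter also records it, though "The Piko-1 will be provided to 20 randomly selected participants from each site (10 from each treatment group"), which is 20 × 3 = 60 of 378 teens. A reader might also infer that exacerbation reports will be mostly zeros. No rate is given, and eligibility requires persistent asthma with health service use in the past year, so that is an assumption. Finally, the plan does not itself name a change-score analysis.

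Two answers remain. The plan need not name a change score, because the treatment-by-time term equals one when there are two readings. And a model-choice sentence with no rule per outcome postpones the decision until the data have been seen; it does not make it.

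**Conclusion.** The point holds as a free improvement. Aim 1 has no method suited to its two-reading outcomes or to exacerbation events, and better standard methods use data already being collected. For objective adherence and FEV1, adjustment for the first reading would need 65% to 85% of the change-score variance over assumed r of 0.3 to 0.7, under equal variances and a first reading unaffected by arm. The second condition is open for FEV1: teens are randomised on enrolment, so the camp reading comes after randomisation, and the plan does not say whether it precedes the instructional sessions. A change score has the same weakness. For exacerbations, the case against transformation is certain for a yes/no item and depends on an unstated event rate for counts; that a linear trend is not a rate or risk does not depend on it.

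These outcomes are exploratory. Nothing here touches the primary quality-of-life analysis.

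**What to change.** Add to Section 10.1, under Aim 1:

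- **Objective adherence and spirometric FEV1:** regress the month-15 value on arm, first reading, site, gender and age stratum. For FEV1, state whether the camp reading is taken before the instructional sessions.
- **Exacerbations:** state whether the checklist is scored as a count or yes/no and over what recall period. Then use a negative binomial or logistic mixed model over the post-camp visits and report a rate ratio or odds ratio by arm.
- **Scales collected at all eight visits:** keep the linear mixed model, and write out its random effects.

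The cost is a few sentences of analysis-plan wording and standard code. No new data or visits are needed.
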